The Effect Of Sacral Massage On Labour Pain and Anxiety: A Randomized Controlled Trial

Objective: This study was conducted as a randomized, control experimental study to determine the effect of sacral massage, on labour pain and anxiety.

Background

Labour is regarded as one of the physiological behaviours in humans that has existed since the beginning of humanity, the formation cycle of which has remained unchanged (Gönenç & Terzioğlu, 2012). Labour is a health state that most women aspire to, at some point in their lives. The first thought that comes to the mind of an expecting woman regarding her delivery is the pain of labour. The pain of the labour is the central and universal part of woman's experience of childbirth. Labour is a normal physiological process, which while should be an occasion for rejoicing, it also accompanies with it, lots of pain, agony, and discomfort and certain risks. Thus although being a joyful and empowering experience it can end with negative and tragic results, leaving the woman filled with fear and anxiety for future birth (Labrecque, Nouwen, Bergeron, & Rancourt, 1999). The causes of labour pain can be either physical or psychological. Physical factors include uterine contractions, cervical dilatations, cervical effacements etc. Psychological factors include fear and anxiety, previous experiences, inadequate support, inadequate knowledge. Pain perceived during labour may be different for each woman (Sethi & Barnabas, 2017). The fear and anxiety that pregnant women experience during the labour process leads to the stretching of pelvic muscles and creates resistance against the repulsive force of the uterus and the repulsive force exerted by the women during labour. The extension of the anxiety-related tension in the pelvic muscles causes general fatigue in pregnant women, increased pain and decreased power to cope with the pain (Gönenç & Terzioğlu, 2012). Feelings of anxiety can cause pregnant women to inappropriately respond and lose their self-control. Anxiety also reduces the self-confidence of an individual. As a result of this situation, pregnant women perceive themselves as incompetent and unskilled. The anxiety experienced during labour directs women to caesarean section by their own will (Fenwick et al., 2010). The essence of midwifery can be with woman providing comfort in labour. Touch communicates caring and reassurance. Manual healing methods used today during delivery include touch and massage therapy. Painful uterine contractions can be treated by applications of pressure with the hands to woman's back, hips, thighs and sacrum. By massage therapy, pharmacological management during the first stage of labour can be reduced. So less negative effects will be

there on foetus and mother (Smith, Levett, Collins,& Jones, 2012). Non-pharmacological and supportive methods that are used to decrease pain are a part of midwifery/nursing practices. Massage is the oldest tactile stimulation method that is used to relieve labour pain. Massage is a manual process performed on the soft tissues of the body for systemic purposes to improve health and well-being. Massage decreases the severity of pain, loosens the spasms and provides general relief during labour (Field, 2010).

METHODS

Study design

This was a randomized and controlled experimental study aimed to determine the effects of sacral massage on labour pain and anxiety.

Setting and samples

The study was performed in volunteer pregnant women who applied to xxx Training and Research Hospital, Delivery Unit, to undergo their first labour between January 25 and October 25, 2016. This unit contains 1 delivery room (with 2 tables), 2 labour follow-up rooms (with 5 beds), 1 postpartum room (with 5 beds) and 1 nursing room.

According to hospital records, in all, 342 pregnant women who applied to xxx Training and Research Hospital, Delivery Unit to undergo their first labour between January 25 and October 25, 2016, constituted the population of the study. The following inclusion criteria were used to determine participation in the study: (1) 19-40-year-old primiparous pregnant women;(2) Singleton pregnancies between 38-42 weeks; (3) Pregnant women whose labour began spontaneously; (4) Pregnant women with a healthy foetus; (5) Pregnant women without any complications that may cause dystocia during labour; (6) Pregnant women for whom analgesia and anaesthesia were not used during the first phase of labour; (7) Pregnant women who volunteered to participate in the research and who could establish verbal communication. In addition, Pregnant women with high-risk pregnancies, with caesarean section indication, and Pregnant women with a chronic illness were excluded.

The sample size was calculated by Medical Faculty Biostatistics Department using Minitab Program. The sample volume to represent the population was determined as minimum 30 people for each group when considering comparison results of mean scores in the study of Field., with a risk of $\alpha= 0.05$, an accuracy rate of $1-\alpha =0.95$ and a power ratio of $B= 0.20$, $1-B= 0.80$ [3].

The study was conducted with two groups, namely Massage Group (experimental), and Control Group. 30 pregnant women were included in each group; therefore, the study was conducted with a total of 60 pregnant women. The women who participated in the study were randomized randomly as control (double) and experimental (single) groups according to the single or double patient admission numbers. The women who participated in the study were randomized into either the control (double) or the experimental (single) group according to single or double patient admission numbers.

Measurements

In this study, the Questionnaire form, Birth action follow-up form, postpartum interview form ,Visual analogue scale (VAS) and State-trait anxiety inventory (STAI FORM TX-I) were used to collect the data.

1. *Questionnaire Form:* Questions that reflect the sociodemographic characteristics of the patients (age, educational status, social security, marital status), information about pregnancy (drugs used, status of their willingness to become pregnant, gestational week, status of attending examinations, status of collecting information about labour), the methods used to cope with the pain, and open-ended questions that evaluate the previous use of massage.

2. *Birth Action Follow-Up Form:* The questions that indicate the length of the first phase, the interventions performed to shorten the first phase of labour, the methods used by the patient to cope with the labour pain, the emotional behaviours of the pregnant women during labour, the length of the second phase, adjustment of the pregnant women, the presence of intervention in labour, the status of episiotomy, the total duration of labour and the baby's health.

3. *Postpartum Interview Form:* Open and closed questions that indicate the pregnant women's thoughts about labour, the status of overall satisfaction with labour and how the women feel were included in this form, which was prepared by a researcher in accordance with the relevant literature.

4. *Visual Analogue Scale (VAS):* The Visual Analogue Scale (VAS) was used to measure the severity of labour pain. On this scale, numbers from 0 to 10 appear on a horizontal line of 100 mm. The pain level is expressed in figures that range from 0 to 10, as follows: the absence of pain is indicated by "0", while the most severe pain is indicated by "10". In this method, it is explained to the individual that there are two endpoints and that he/she is free to mark any point that defines his/her pain.

The VAS was applied to the participants in the control group once in the latent (3-4 cm), active (5-7 cm) and transition phases (8-10 cm) of labour. The VAS was also applied to those in the experimental group once after the massage in each phase. The diagnosis was made in accordance with the subjective data including the patient's verbal expression.

5. State-Trait Anxiety Inventory (STAI FORM TX-I): To determine state and trait anxiety levels of the participants, the state-trait anxiety inventory (STAI FORM TX -I) was used. The individual is required to indicate the feelings or behaviours that he/she has experienced in a specific situation according to the degree of severity by marking one of the options such as (1) Never, (2) Little, (3) Very and (4) Completely. The state-trait anxiety inventory requires the individual to describe how he/she feels at a certain moment and under certain conditions by considering his/her feelings about a specific situation. While high scores indicate high anxiety levels, low scores indicate low anxiety levels. The state-trait anxiety inventory consists of 20 statements. The score obtained from the scale may vary between 20 and 80. While a high score represents a high anxiety level, a low score represents a low anxiety level. In the scoring performed in accordance with the criteria directive, 0-19 points are regarded as "none", 20-39 points are regarded as "mild anxiety", 40-59 points are regarded as "moderate anxiety", 60-79 points are regarded as "heavy anxiety" and 80 points are regarded as "severe anxiety". In our study, the STAI FORM TX-I was used in the active (5-7 cm) phase in the control group and in the active (5-7 cm) phase after the massage in the experimental group to evaluate the anxiety experienced by women during labour.

Data Collection

After approval and permission to conduct the study were obtained from the ethics committee, the hospital's head nurse, delivery room charge nurse/midwife and other midwives and nurses were interviewed and informed about the purpose and scope of the study. Data were collected by one of the researchers. The researcher was aware of which patients were assigned to each group. However, the researchers did not interfere in any way with the study results. When they encountered women who met the inclusion criteria of the study, the purpose of the study was explained, and written consents were received from those who agreed to participate in the study. For the women who satisfied the criteria, participation in the study was voluntary. Additionally, during the study, no women requested to withdraw and no women were excluded from the study. Routine care and treatments for the women continued during data collection.

Procedure

Before the research data were collected, an informative meeting regarding the purpose and scope of the study was held for the members of the healthcare team who worked in the obstetrics and gynaecology clinic of the Turkish Republic Ministry of Health Public Hospitals Administration of Turkey, at the Istanbul Province xxx Training and Research Hospital, where the study would be conducted. In addition, cooperation was provided by the members of the healthcare team. For the correct application of the massage, the researcher was trained by the physical therapist who work at hospital. The massage was applied only to the pregnant women in the intervention group at every phase of labour. There was no intervention in the control group except for routine hospital applications. The steps taken in this study are discussed below.

For the pregnant women included in the experimental group:

- One-on-one interviews were conducted with the pregnant women, and the voluntary disclosure forms, which explained the purpose of the study, were completed.
- The prepared questionnaire form was applied.
- In addition to providing them with routine nursing/midwifery care, the women in the experimental group were administered a massage to the sacral region under the supervision of a doctor for 30 minutes using the effleurage (patting) (15 minutes) and vibration technique (15 minutes) in the latent (3-4 cm), active (5-7 cm) and transition (8-10 cm) phases of labour. To achieve this, the patients were placed in the left lateral position in the latent (3-4 cm), active (5-7 cm) and transition (8-10 cm) phases of labour.
- The state-trait anxiety inventory (STAI FORM TX-I) was applied and evaluated after the massage in the active (5-7 cm) phase.
- The Visual Analogue Scale (VAS) was evaluated once after the massage in the latent (3-4 cm), active (5-7 cm) and transition (8-10 cm) phases.
- Birth action follow-up form and postpartum interview forms were applied.

For the pregnant women included in the control group:

- One-on-one interviews were conducted with the pregnant women, and the voluntary disclosure forms, which explained the purpose of the study, were completed.
- The prepared questionnaire form was applied.

- Routine nursing/midwifery care was applied.
- The state-trait anxiety inventory (STAI FORM TX-I) was applied and evaluated in the active (5-7 cm) phase.
- The Visual Analogue Scale (VAS) was evaluated once in the latent (3-4 cm), active (5-7 cm) and transition (8-10 cm) phases.
- Birth action follow-up form and postpartum interview forms were applied

One-on-one interviews were conducted with the women in both groups, and the voluntary disclosure forms, which explained the purpose of the study, were completed. After the prepared questionnaire form was applied to the women in the experimental group, routine nursing/midwifery care was provided.

Hypotheses of the Study

1. Massage applied to the sacral region decreases the perception of a woman's labour pain.
2. Massage applied to the sacral region decreases the woman's levels of concern and anxiety about labour.
3. Massage applied to the sacral region increases the woman's satisfaction with the labour.

REFERENCES

Field, T. (2010). Pregnancy and labor massage. Expert Review of Obstetrics & Gynecology, 5(2):177–181.

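### Allocation by odd or even admission number is a predictable rule, not randomization, yet the protocol calls the study randomized

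*Protocol*

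**What the plan says.** The title is "The Effect Of Sacral Massage On Labour Pain and Anxiety: A Randomized Controlled Trial". The Objective repeats the label ("This study was conducted as a randomized, control experimental study"), and so does Study design ("This was a randomized and controlled experimental study aimed to determine the effects of sacral massage on labour pain and anxiety").

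The mechanism is under Setting and samples, where it is stated twice in nearly the same words: women were "randomized into either the control (double) or the experimental (single) group according to single or double patient admission numbers". The same section gives the source population ("According to hospital records, in all, 342 pregnant women") and the group sizes ("30 pregnant women were included in each group; therefore, the study was conducted with a total of 60 pregnant women").

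Under Data Collection, recruitment is described as "When they encountered women who met the inclusion criteria of the study, the purpose of the study was explained", followed by written consent. On blinding, the text says "The researcher was aware of which patients were assigned to each group".

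Under Measurements and Procedure, pain (VAS) and anxiety (STAI) in the experimental group are recorded only after massage. The SAP's Data analysis section names descriptive statistics, the chi-square test and Student's t-test at p < 0.05. It lists background items as independent variables, but specifies neither a comparison of them between groups nor an adjusted model.

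**The concern.** A reader of a randomized trial expects the assignment to come from a chance process and, with concealment, expects that the decision to enter a woman could not depend on her arm. An odd/even rule supplies no chance process, and nothing in the text hides the coming assignment. If the recruiter could see the admission number before approaching a woman or taking consent, the arm was known at that point.

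Both main outcomes are subjective self-reports. If women entered to massage were, even unintentionally, calmer or in less pain, the difference would appear as a massage effect. With no score before massage in the experimental group, selection on baseline pain, baseline anxiety or unmeasured prognosis would leave no trace in the data. What is at stake is how strongly a difference with p < 0.05 can be attributed to massage.

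**Working it through.** **1. Label against mechanism**

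| Place in protocol | What it states |
|---|---|
| Title | randomized |
| Objective | randomized |
| Study design | randomized |
| Setting and samples | randomized, by odd or even admission number (stated twice) |

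I read *single* and *double* as odd and even; no other reading fits. The available text describes no random list, computer generation, envelopes, central allocation or independent allocator. Someone who sees the number predicts the arm with probability 1. Under concealed simple 1:1 randomization the probability is 0.5.

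**2. What the documents leave open**

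They do not say what the admission number is (a hospital number or an order of entry). They do not say when the researcher learned it relative to approach and consent, or how exactly 30 per group was reached. Data Collection shows directly only that the data collector was unblinded. Prior knowledge of the arm is possible but not established.

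**3. Room for selection**

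Enrolled: 60/342 = 17.5%. Not enrolled: 342 − 60 = 282. The 342 are all women admitted for a first labour in the period. The 282 are not divided into ineligible, not approached and refused.

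**4. The 30:30 split**

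Assume a hospital number, odd and even equally likely, and no limit per group. Then P(exactly 30 of 60) = C(60,30)/2^60 = 0.103. Drawing without replacement from an assumed 171 odd and 171 even numbers gives 0.113. An equal split is compatible with the rule and is not evidence of selection. A stop at 30 per group, or numbering by order of entry, would also produce it.

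**5. Illustration of bias (shifts are assumptions)**

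No true effect; n = 30 per group; Student's t-test with df = 58 and alpha 0.05; selection shifts the group difference by s SD in favour of massage. The noncentrality parameter is s/√(2/30) = s × √15. The SAP does not state sidedness, so both are shown.

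| Assumed shift s | s × √15 | False-positive rate, two-sided | One-sided |
|---|---|---|---|
| 0.1 SD | 0.387 | 6.7% | 10.3% |
| 0.2 SD | 0.775 | 11.9% | 19.0% |
| 0.4 SD | 1.549 | 33.2% | 45.5% |

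**6. What a covariate table can show**

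The 95% half-width for a difference in means of a continuous item is 2.002 × √(2/30) = 0.517 SD. By the same calculation as in step 5, a true covariate imbalance of 0.4 SD would reach two-sided p < 0.05 only 33% of the time. A non-significant comparison therefore does not demonstrate balance.

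**The case against.** The strongest reply is that whether an admission number is odd or even is probably unrelated to a woman's prognosis, so among all admissions the rule may behave much like chance, and nothing shows that anyone used it to select. The second half stands: selection is not shown. The first half does not rescue the label, because the difficulty is predictability at entry, and 60 of 342 women were entered.

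Sequence generation and concealment are also separate matters. A truly random but openly posted list would still be randomized. That is fair, but this rule has no random sequence in the first place, so the label fails before concealment is considered. Part of the protocol's text was not available to review, so a concealment step may exist there. The sponsor should confirm this, but concealment would not turn an odd/even rule into a random sequence.

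The SAP's chi-square test may have been meant for comparing background items between groups. That is a plausible reading, but the section does not say so, and p-values alone would be weak evidence of balance at this size.

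Finally, the shifts in the illustration have no source in the documents, and the minimum of 30 per group in the sample-size paragraph makes a per-group stop an ordinary explanation of the equal split. Both points are accepted, and the conclusion rests on neither figure. The missing scores before massage would be a weakness under any allocation; they matter here because they remove the means of detecting selection.

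**Conclusion.** The concern holds, and the label must be corrected. The protocol claims a property that its own allocation sentence contradicts: the rule is deterministic, and no random sequence or concealment step is described. The study as documented is quasi-randomized, and a difference at p < 0.05 cannot be attributed to massage with the strength that randomization would allow.

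This rests on the wording alone: on reading single/double as odd/even, and on the available text being complete on this point. The size of any bias is unknown. The false-positive rates of about 7% to 33% two-sided, or 10% to 45% one-sided, apply only to the assumed shifts of 0.1 to 0.4 SD.

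**What to change.** 1. **Relabel.** Use *quasi-randomized (allocation by odd/even admission number)* in the title, Objective, Study design and Setting and samples, where the rule appears twice. Suggested allocation text, once the sponsor has confirmed it: *Women with odd admission numbers were allocated to massage and women with even numbers to control; no random sequence was used.* If a random sequence or a concealment procedure was in fact used, document it instead. Add what the admission number is, when the researcher learned it relative to approach and consent, and how 30 per group was reached. State that no concealment was used only if that is confirmed.
2. **State the limitation.** Name predictable allocation and the absence of pain and anxiety scores before massage. Do not attribute differences to massage with the strength of a randomized comparison.
3. **Tabulate the questionnaire items by group**, giving differences with 95% intervals and not only p-values. Working status and husband's education are in the SAP list but are not named in the questionnaire description, so include them only if they were recorded. Report numbers eligible, approached, refusing and enrolled by odd/even number if records exist.
4. **Optional sensitivity analysis, labelled post hoc.** Adjust VAS scores, STAI score and phase durations for the three items named in both the questionnaire description and the SAP: age, educational status and willingness to become pregnant. State that this cannot remove selection on unmeasured distress.

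**Cost.** Wording changes in four places, one limitation paragraph and one table from questionnaire data already collected. Flow numbers depend on screening records, which the documents do not mention beyond the count of 342. No new patients or visits are needed. The study loses the randomized label.

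### Self-reported pain and anxiety were collected by a researcher who knew the allocation and apparently also gave the massage, with no described safeguard; the researcher's share of any bias can be reduced cheaply, by an unknown amount

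*Protocol*

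**What the plan says.** **Who collects, and what they know.** Protocol, Data Collection: "Data were collected by one of the researchers", followed by "The researcher was aware of which patients were assigned to each group". The only answer given to this is the next sentence: "However, the researchers did not interfere in any way with the study results".

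**Who gives the massage.** Protocol, Procedure: "For the correct application of the massage, the researcher was trained by the physical therapist who work at hospital". The steps for the experimental group describe the massage in the passive voice, under a doctor's supervision, and do not name who gave it.

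**How the scales are completed.** Protocol, Measurements, item 4 (VAS): the woman is shown a 100 mm line and told that "he/she is free to mark any point that defines his/her pain". The same item then ends with: "The diagnosis was made in accordance with the subjective data including the patient's verbal expression". Item 5 (STAI) has her answer 20 statements "by marking one of the options such as (1) Never, (2) Little, (3) Very and (4) Completely".

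**When, and by whom.** The VAS is taken once in each of three phases and the STAI once in the active phase, after the massage in the experimental arm and during routine care in the control arm. The Procedure steps say that the instruments were administered and evaluated, but not by whom.

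**What is absent.** Neither the Protocol nor the SAP describes private completion, coded forms, masked measuring or summing, or an analysis masked to arm.

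**The concern.** Pain and anxiety are the outcomes in the trial's title and in hypotheses 1 and 2. Both are subjective, so contact with the person taking the rating can affect it, and that contact differs by arm. A massaged woman rates her pain just after treatment, apparently for the person who treated her. A control woman has had routine care only.

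There are three possible routes of influence: prompting at the moment of rating, an answer meant to please the therapist, and judgement by an unmasked person in reading or recording the answer. The third depends on what the sentence about the diagnosis means. If it describes how the pain score was set, an unmasked judgement may have entered the number. If it does not, the score is simply her mark.

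Such influence would plausibly favour massage, though its direction is not documented. The Student's t-test in the SAP compares arm means and cannot separate a reporting shift from a massage effect.

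**Working it through.** **Inputs from the documents.** 30 women per arm, alpha 0.05 and power 0.80 (Protocol, Setting and samples); Student's t-test at p < 0.05 (SAP, Data analysis). The documents give no mean difference, no SD and no statement of one- or two-sided testing. I take two-sided.

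**The plan's own figure.** The 30 per arm cannot be reproduced without an effect size and SD. It can only be inverted: at 80% power a two-sided t-test with 30 per arm detects a standardised difference of about 0.74. The smallest observed difference that reaches significance is t(0.975, 58) × √(2/30) = 2.002 × 0.2582 = 0.517 SD.

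**Sensitivity to a reporting shift.** Let the true effect be zero and let reporting move one arm by b SD. The t statistic then follows a noncentral t distribution with 58 degrees of freedom and noncentrality b × √(30/2) = b × 3.873. The false-positive rate is the probability that it falls outside ±2.002.

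| Assumed shift b (SD) | Noncentrality | Rejects in favour of massage | Rejects in either direction |
|---|---|---|---|
| 0 | 0 | 2.5% | 5.0% |
| 0.10 | 0.387 | 5.7% | 6.7% |
| 0.25 | 0.968 | 15.7% | 15.9% |
| 0.50 | 1.936 | 47.8% | 47.8% |

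The third column takes the shift to favour massage.

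**On the VAS scale.** The documents give no SD. If it were 1.5 to 2.5 points (an assumption), a shift of 0.5 points would give a false-positive rate of 25% down to 12%, and a shift of 1 point 72% down to 33%.

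**What the table does not show.** Every shift in it is assumed. The calculation does not divide a shift between the researcher's influence and the woman's own knowledge of her group, so it does not measure what the fix would gain.

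**The case against.** **The woman marks both scales herself.** This is correct and it limits the point. Masked scoring then removes only errors in measuring, summing and entry. Private completion reduces prompting at the moment of rating, but not influence exerted earlier, in the interview, in explaining the study's purpose or during the massage.

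**The women cannot be masked.** Massage is compared with routine care, so each woman knows which she received. Expectation and attention effects on self-report remain whatever is done about the researcher. This stands in full. A reader might infer that private completion and masked scoring would remove most of the bias; nothing in the documents supports that.

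**The collector is not said to be the therapist.** Two mentions of the researcher in adjoining sections suggest one person, but the text also speaks of several researchers and describes the massage in the passive. The identity is likely, not established. The masking problem does not depend on it.

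**The sentence about the diagnosis may not concern the score.** A reader might infer that an unmasked judgement set the pain score. The Protocol does not define the term or link it to the number analysed, and a woman's verbal expression is still her own report. What stands is that the sentence is ambiguous.

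**Someone else would have to help or score.** Handing the task to a ward midwife would only move the unmasked contact, since the midwives were briefed on the study and work on the unit. Masked scoring needs a person other than the collector. The Protocol implies that there are other researchers but does not state their availability, so a cost of nothing in staff time is not shown.

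**The data may already exist.** The Protocol is written in the past tense and gives a recruitment period of January to October 2016. If collection is finished, private completion cannot be applied to these women.

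**Conclusion.** The point holds in a limited form. A researcher who knew the allocation collected the subjective outcomes behind hypotheses 1 and 2, and the documents offer an assurance where a procedure is needed. Researcher influence could enter both outcomes, and the wording on how scores were obtained is too loose to exclude it.

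The false-positive range of 6.7% to 48% assumes a shift of 0.10 to 0.50 SD, no true effect, 30 per arm and a two-sided 0.05 t-test. It shows that a modest shift could produce a significant result. It is not an estimate of the bias in this trial, and the documents do not support reading it as evidence that the results are false or that scores were altered.

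The change below would reduce the researcher's part of any bias by an amount that cannot be computed. It is worth making because it costs little and leaves sample size, treatment and test unchanged. Confidence is medium: the lack of masking is stated outright, but its effect is not known.

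**What to change.** 1. **Completion (Protocol, Measurements and Procedure).** The woman marks the VAS and completes the STAI herself, out of the researcher's sight, and seals the form. The form carries a study code that cannot be traced to the admission number: allocation follows odd or even admission numbers, so a traceable code would reveal the arm. Any help follows a fixed script and is recorded, with the helper's role.
2. **Definition of the score (Measurements, item 4).** State what the sentence about the diagnosis refers to; removing it without explanation could hide what was done. Define the pain score solely as the distance in millimetres to her mark. State who administers and who scores each instrument.
3. **Scoring and analysis (Data Collection; SAP, Data analysis).** Another member of the existing research team, masked to arm, measures the marks and sums the STAI. The analysis runs with arms coded A and B until the tables are final.

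If data collection is complete, apply items 2 and 3 to the retained forms, and report unmasked collection as a limitation. If the original forms were not kept, masked re-scoring is not possible and the report should say so.

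In either case, state as a limitation that the women knew their group and that expectation and attention effects remain.

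**Cost.** Envelopes, a short script, a coded data file and a little of a colleague's time. Some women in the transition phase may be unable to complete the form without scripted help, which is why its use should be recorded by arm.
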